7.5 Analysis Populations

7.5.1 Definitive and Supplemetal

Due to GCP non-compliance at site 201, it was decided to exclude data from that site from the Definitive Efficacy Analysis. A Supplemental Efficacy Analysis will be presented including the data from site 201.

The mITT and PP populations defined below will not inlcude site 201. However, there will be a supplemental mITT population (mITTs) and a supplemental PP population (PPs), both of which will include site 201.

7.5.2 Screen Failures

Investigators must account for all subjects who sign informed consent and will maintain an Enrollment Log capturing subjects screened and indicating who was enrolled or excluded and the reason why. If the subject is found not to be eligible prior to enrollment, the reason(s) for ineligibility must be documented by the Investigator.

These subjects will neither contribute to data presentations nor be included in formal statistical analyses. The number of screen failures will be included in the data disposition table. Subject Numbers assigned to subjects who fail Screening will not be re-used.

Protocol: 16-POD-001 Version 2.0, 15-Jan-2018

Confidential

7.5.3 **Protocol Deviations**

A deviation is defined as an "unintentional and/or accidental change to, or non-adherence to, the IRB/EC approved trial protocol (Biorasi SOP CL-035)." Protocol deviations will be documented for randomized subjects as well as screen failures in this trial.

- Minor Protocol Deviation defined as any change, divergence, or departure from the IRB/IEC Approved Trial Protocol, criteria or procedures that does not affect the Subject's safety, rights, or welfare and/or the integrity of the Trial and its resultant data.
- Major Protocol Deviation defined as any change, divergence, or departure from the IRB/IEC Approved Trial Protocol, criteria or procedures that may affect the Subject's safety, rights, or welfare and/or integrity of the Trial and its resultant data.

Prior to database lock, there will be a joint classification meeting held between the Sponsor, Data Management, Biostatistics, and Clinical in order to classify protocol deviations and patient classification. This information will be added to the PVPD log and utilized for setting the population flags for analysis.

Any subject adjudication to the PP population and mITT population should be supported by Data Management according to protocol and take into consideration the PVPD log provided by Principal Investigators. Subjects who experience a Major Deviation will be excluded from the PP population.

7.5.4 Safety Population

The safety population includes all randomized subjects who received and used study product.

7.5.5 Modified Intent-to-Treat (mITT) Population

The modified intent-to-treat population (mITT) includes all subjects who are randomized, applied at least one dose of assigned product, and returned for at least one post-baseline evaluation visit. Subjects discontinued prematurely from the study for any reason other than Treatment Failure, (i.e., noncompliance, withdrawal of consent, etc.) will be included in the mITT population, using Last Observation Carried Forward (LOCF).

7.5.6 Per-Protocol (PP) Population

All randomized subjects who met all inclusion/exclusion criteria, had no protocol violations that would affect the treatment evaluation , were compliant with applying study product, and returned to the study site for the primary endpoint evaluation at 4 days (\pm 5 days) after the last day of the last cycle of treatment. Compliant subjects are defined as those who used

Protocol: 16-POD-001 Version 2.0, 15-Jan-2018

Confidential

at least 75% and no more than 125% of study drug doses until treatment success or four cycles of treatment.

Subjects discontinuing due to "treatment failure" will be included in the PP population analysis as Treatment Failures and will have alternative treatment recommended by the Investigator.

The results in the PP population will be considered definitive for therapeutic equivalence and those in the mITT population considered supportive. The results in the mITT population will be considered definitive for superiority analysis of each active treatment to placebo and those in the PP population will be considered supportive. Safety analyses will be performed using the Safety population.

7.6 Baseline Definition

The Baseline visit (Day 0) will take place once the results of Screening assessments are obtained, suggesting that the subject is eligible for entering the study. During this visit, those subjects who qualify for entering the study will be randomized to one of the study arms in a ratio of 3:3:1.

Derived and Transformed Data.

7.6.1 Baseline Age

Subject's age in years will be calculated based on the date of the Baseline Visit date using the following formula:

Age (years) = FLOOR((INTCK('month', Date of Birth, Date of Baseline Visit) - (DAY(Date of Baseline Visit) < MIN(DAY(Date of Birth), DAY (INTNX ('month', Date of Baseline Visit, 1) -)))/12)17 where:

•FLOOR() is a SAS function that returns the largest integer that is less than or equal to the argument.

•INTCK() is a SAS function that returns the number of interval boundaries of a given kind that lie between two dates, times, or datetime values.

•DAY() is a SAS function that returns the day of the month from a SAS date value.

•INTNX() is a SAS function that increments a date, time, or datetime value by a given time interval, and returns a date, time, or datetime value.

STATISTICAL ANALYSIS PLAN

Confidential

7.6.2 Study Day

•Day 1 is defined as the day after the baseline when the subject will receive the first dose.

•For a visit date on or after the date of the first dose: Study Day = (date of interest – date of first dose) + 1

•For a visit date before the date of the first dose: Study Day = (date of interest – date of first dose)

7.6.3 Visit Windows

Visit windows for study 016-POD-001 are as follows:

Study Phase	Visit	Visit Name	Day
Screening	Visit 1	Screening	-14 to -1 days
Baseline	Visit 2	Baseline	Day 0
Follow-up	Visit 3	1 st Follow-up Visit (FU 1)	Day 7 (±1)
	Visit 4	2 nd Follow-up Visit (FU 2)	Day 14 (±1)
	Visit 5	3 rd Follow-up Visit (FU 2)	Day 21 (±1)
	Visit 6	End of Study	Day 28 (±5)
End of Study ¹	EOS	End of Study	Day1 – Day 28 (+5)
	ET	Early Termination Visit	From Screening to Day 28
	US	Unscheduled Visit	From Screening to Day 28 (+5)

1. If total disappearance of all warts is achieved within all treated areas at visits 2, 3, 4, or 5, respective visit will be considered an End of Study (EOS) visit.

Confidential

The flowchart for the study is as follows:

7.6.4 Multiple Assessments

No multiple assessments for same visit are scheduled.

7.6.5 Handling of Missing Data

No data will be imputed for the Safety population. Missing Data for Efficacy analyses will not be imputed for the PP population. However, if data is missing due to other than early termination because of treatment failure, it will be imputed as LOCF for the mITT population.

7.6.6 Missing Start and Stop Dates for Prior and Concomitant Medication

Start date:

- 1. If start date is completely missing, start date will not be imputed.
- 2. If (year is present and month and day are missing) or (year and day are present and month is missing), set month and day to January 1.
- 3. If year and month are present and day is missing, set day to the 1st day of month.

Stop date:

- 1. If end date is completely missing, end date will not be imputed.
- 2. If (year is present and month and day are missing) or (year and day are present and month is missing), set month and day to December 31st.
- 3. If year and month are present and day is missing, set day to the last day of month.

7.6.7 Missing Start and Stop Dates for Adverse Events

Start date:

1. If start date is completely missing, start date is set to date of first dose.

Confidential

- 2. If (year is present and month and day are missing) or (year and day are present and month is missing):
 - a. If year = year of first dose, then set month and day to month and day of first dose.
 - b. If year < year of first dose, then set month and day to December 31st.
 - c. If year > year of first dose, then set month and day to January 1st.
- 3. If month and year are present and day is missing:
 - a. If year = year of first dose and
 - i. If month = month of first dose, then set day to day of first dose date.
 - ii. If month < month of first dose, then set day to last day of month.
 - iii. If month > month of first dose, then set day to 1st day of month.
 - b. If year < year of first dose, then set day to last day of month.
 - c. If year > year of first dose, then set day to 1st day of month.

Stop date:

If the outcome of the AE was ongoing or unknown, then the rules outlined below will not be applied.

- 1. If stop date is completely missing, stop date is set to date of study discontinuation.
- 2. If (year is present and month and day are missing) or (year and day are present and month is missing):
 - a. If year = year of study discontinuation, then set month and day to month and day of study discontinuation.
 - b. If year < year of study discontinuation, then set month and day to December 31st.
 - c. If year > year of study discontinuation, then set month and day to December 31st.
- 3. If month and year are present and day is missing:
 - a. If year = year of study discontinuation and
 - i. If month = month of study discontinuation, then set day to day of study discontinuation date.
 - ii. If month < month of study discontinuation, then set day to last day of month.
 - iii. If month > month of study discontinuation, then set day to last day of month.
 - b. If year < year of study discontinuation, then set day to last day of month.
 - c. If year > year of study discontinuation, then set day to last day of month.

Confidential

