7.4 Adverse Event Collection Period

Any AE/SAE prior to the Screening visit will be considered past medical history (PMH). The AE reporting period for this study begins with the signature of the Informed Consent Form and, for unresolved AEs, ends 30 days following the last study medication application. Those events that occur during the screening period and up to the day of the first application of the study drug will be considered Non-Treatment Emergent AEs.

Adverse events that occur during the treatment period (starting from the day of the first application of Study Drug and up to the final protocol required visit) will be considered Treatment Emergent AEs (TEAEs).

SAE(s) that are observed or spontaneously reported during the subject's participation in the trial will be captured and monitored until the Investigator deems the event to be chronic or not clinically significant or the subject to be stable.

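### The adverse-event start-date rules in SAP 7.6.7 ignore a recorded stop date, so an event that ended before dosing can get a start after its stop and may be counted as treatment-emergent

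*SAP*

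**What the plan says.** SAP 7.6.7 imputes adverse-event start dates by how much of the date is known.

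- Rule 1, nothing known: "If start date is completely missing, start date is set to date of first dose".
- Rule 2a, month missing: "If year = year of first dose, then set month and day to month and day of first dose". Under rule 2b, an earlier year gives 31 December.
- Rule 3a(i), only the day missing and the year the same as first dose: "If month = month of first dose, then set day to day of first dose date".
- Rule 3a(ii), an earlier month in that year: "If month < month of first dose, then set day to last day of month". Rule 3b does the same for an earlier year.

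No start-date rule refers to the stop date. The one exception, "If the outcome of the AE was ongoing or unknown, then the rules outlined below will not be applied", stands under the stop-date rules and governs only those.

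Protocol 7.4 fixes when events are collected and how they are classed. "The AE reporting period for this study begins with the signature of the Informed Consent Form", and events in screening "up to the day of the first application of the study drug will be considered Non-Treatment Emergent AEs". SAP 10.1.1 summarises treatment-emergent events from the first dose on Day 1. SAP 7.6.5 rules out imputation in the Safety population, which does not fit with 7.6.7.

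**The concern.** Setting an unknown start to first dose is a reasonable cautious default when the timing is truly unknown. When the recorded stop is before first dose, the timing is known: the event is pre-treatment. The SAP already respects that kind of evidence when it comes from the start date, since rules 2b, 3a(ii) and 3b keep an event before dosing if its partial start shows that it belongs there. A stop date is just as decisive, but the rules do not use it.

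Two faults can follow. The derived record can have a start after its stop. An event that the protocol defines as non-treatment-emergent can also enter the treatment-emergent tables (14.3.8 to 14.3.8.2). Safety is the secondary objective and is assessed by the frequency and severity of adverse events, so these tables are the trial's main safety output.

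**Working it through.** The plan gives no figure to reproduce. The check applies the written rules to every event of the kind at issue.

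**Inputs**
- Screening is Day -14 to -1 and Baseline is Day 0 (SAP 3.1). First dose is Day 1, the day after Baseline (SAP 7.6.2). Consent can therefore be up to 15 calendar days before first dose.
- Adverse events are assessed at Screening and at Baseline (Protocol 6.3.1 and 6.3.2), so an event can begin and end before dosing.
- Assumptions: first dose on each of the 365 days of 2018, all combinations equally weighted, and the stop date fully known.

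**Grid.** Let the true start be *s* days and the stop *e* days before first dose, with 1 ≤ e ≤ s ≤ 15. There are 15 × 16 / 2 = 120 pairs, and 120 × 365 = 43,800 combinations.

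**Start fully missing (rule 1).** Every start becomes the first-dose date, and every stop is earlier: 43,800 / 43,800 = 100%.

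**Only the year known (rules 2a, 2b).** The start escapes rule 2a only if it lies in the previous year, that is, if first dose is on 1 to *s* January. For each *s* there are *s* such dates and *s* possible stops, so the number of escapes is 1² + … + 15² = 15 × 16 × 31 / 6 = 1,240.
- Moved to first dose: 43,800 − 1,240 = 42,560, or 97.2%.
- Among the 1,240, rule 2b gives 31 December. That is after the stop when first dose is on day *d* of January and d < e ≤ s: 16 × 15 × 14 / 6 = 560 cases, or 1.3% of 43,800.

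**Only the day missing (rules 3a(i), 3a(ii), 3b).** The same count applies at each of the 12 month boundaries. A lag of at most 15 days crosses at most one of them.
- Start in an earlier month: 12 × 1,240 = 14,880.
- Moved to first dose: 43,800 − 14,880 = 28,920, or 66.0%.
- Kept before dosing but set to a month-end after the stop: 12 × 560 = 6,720, or 15.3%.

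| Known part of start | Moved to first dose | Start after stop, still pre-dose |
|---|---|---|
| None | 100% | – |
| Year | 97.2% | 1.3% |
| Month and year | 66.0% | 15.3% |

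A direct run of the coded rules over the same grid gave the same counts.

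**Examples.** With first dose on 20 March 2018, a stop on 14 March and the start missing, the imputed start is 20 March and the duration is 14 − 20 + 1 = −5 days. With first dose on 3 April 2018, a start in March (day missing) and a stop on 25 March, the imputed start is 31 March. That is before dosing, but six days after the stop.

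**With a guard.** If every imputed start is capped at the recorded stop, 0 of 43,800 combinations in each row reach first dose or have a start after the stop.

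**The case against.** **Treatment-emergent status is inferred.** Neither document says that the flag uses the imputed start. SAP 10.1.1 and the footnote to Table 14.3.8 speak of events reported from first dose or during the treatment period, and an event that had ended and was recorded at Baseline was reported before that. This stands. A reader might infer that such events are certain to enter the treatment-emergent tables. The documents support only a conditional statement: they enter if status is derived from the imputed start, which is the likely use of the rule. The start-after-stop fault does not depend on this.

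**SAP 7.6.5 rules out imputation for the Safety population.** Taken alone, it would remove the problem. But 7.6.7 is the specific rule and would serve no purpose if 7.6.5 overrode it. The conflict is a further reason to edit the text.

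**The trigger is narrow.** Protocol section 7 requires the date of onset for every event, so a missing start with a known pre-dose stop should be uncommon. This stands. A reader might take the percentages as the share of adverse events affected, but the documents give no count of missing dates.

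**The consequence is small.** Safety reporting is descriptive. These events precede dosing in a blinded, randomised trial, so no direction between arms is expected. No planned table reports event duration. This also stands, and nothing in the documents supports reading the point as a bias between arms or a threat to the equivalence or superiority results. Nor do they describe any date checks that such records would fail.

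**Over-counting is conservative.** SAP 10.1.1 does take the worst case for missing severity or relationship. That argument fails here because the needed information is not missing: the stop date settles the timing.

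**A quick estimate of the same-month share is too high.** Using the mean lag of 8 days for any event starting 1 to 15 days before dosing gives 1 − 8/30.4 = 0.74. The events at issue must also have ended before dosing, so they start earlier: the mean lag on the grid is 1,240 / 120 = 10.3 days, and 1 − 10.3/30.4 = 0.66. Protocol 6.1.1 also allows for wash-outs of more than 30 days after consent. Longer gaps would lower the share further.

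**Conclusion.** The point holds as a gap in the rule. Rules 1, 2a and 3a(i) place the start of an event that ended before dosing after its stop, and make it treatment-emergent if status follows the imputed start. Rules 2b, 3a(ii) and 3b keep the event before dosing but can still place the start after the stop. Both faults arise only when the recorded stop is before first dose.

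The grid results (100%, 97% and 66% moved to first dose, and a further 15% of day-missing cases with start after stop) rest on equal weights, a gap of 1 to 15 days and 2018 dates. They show how the rules behave once triggered. How often they are triggered is unknown and probably rare.

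For scale, one misclassified subject adds 1/59 = 1.7 percentage points in the placebo arm and 1/177 = 0.6 points in an active arm, at the enrolment planned in SAP 5.3. This is a minor clarification that would be good to make. It touches only descriptive safety tables and listings.

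**What to change.** Add to SAP 7.6.7:

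1. Under every start-date rule, no imputed start may be later than the recorded stop date.
2. First-dose imputation applies only if the stop date is missing, ongoing, or on or after first dose. A partial stop date counts as before first dose only if its known parts show this.
3. An event with a stop before first dose is non-treatment-emergent.

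The cap has to cover every start-date rule. A guard on first-dose imputation alone would leave the 15.3% of day-missing cases that arise through the month-end rules.

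In the same edit, reconcile 7.6.5 with 7.6.7, for example by stating that the ban on imputation in the Safety population does not extend to the date rules.

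The cost is a few sentences and about one line of code. The change belongs in the SAP and should not be left to the programmer, because SAP 7.4 requires true differences in data handling to be documented.

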8 STUDY POPULATION

8.1 Subject Disposition

The subject disposition summary will include the number screened, the number of screen failures, the number enrolled, the number in each patient population for analysis, the number who completed the study, the number who discontinued the study and reason for discontinuation from the study. Disposition data will be summarized by treatment and overall.

A by-subject data listing of study completion information including the reason for study discontinuation will be presented. A by-subject listing of inclusion/exclusion criteria not met will also be presented.

8.2 **Protocol Deviations**

A summary of all protocol deviations by type will be generated. Protocol deviation data will be summarized by treatment and overall. A by-subject data listing of protocol deviations will also be presented.

Any subject adjudication to the PP population and mITT population should be supported by Data Management according to protocol and take into consideration the PVPD log provided by Principal Investigators.

8.3 Demographic and Baseline Characteristics

Descriptive statistics will be generated by treatment group for selected continuous variables. The number and percentage of subjects in each class of categorical demographic and baseline variables (e.g., gender, ethnicity, and race) will be tabulated by treatment group. Individual subject demographic and baseline characteristic data will be listed.

8.4 Medical History

A by subject data listing of medical history will be presented.

D-001 STATISTICAL ANALYSIS PLAN

Protocol: 16-POD-001 Version 2.0, 15-Jan-2018

Confidential

9 EFFICACY ANALYSES

9.1 Primary Efficacy Endpoint

The primary endpoint is the proportion of subjects with "treatment success" defined as "total disappearance of all warts within all treated areas." The primary endpoint will be evaluated at 4 days (\pm 5 days) after the last day of the last cycle of treatment. The results of analysis for bioequivalence in the PP population will be considered definitive and those in the mITT population as supportive.

Due to GCP non-compliance at site 201, it was decided to exclude data from that site from the Definitive Efficacy Analysis. A Supplemental Primary Efficay Analysis will be presented including the data from site 201.

9.1.1 Bioequivalence Analysis

The efficacy bioequivalence of the test and reference treatments will be based on the proportions of subjects with clinical success. The hypothesis tested for clinical equivalence between test and reference will be:

Bioequivalence between the test and the reference product will be established if the 90% confidence interval for the difference in success proportions is contained within the equivalence limits [-0.20, +0.20].

In this case, the compound hypothesis to be tested is:

 $H_0: P_T - P_R < -0.2$ or $P_T - P_R > 0.2$ (meaning test product is not bioequivalent to the reference);

versus

 $H_a: -0.2 \leq P_T - P_R \leq 0.2$ (supporting bioequivalence);

where P_T = success proportion of test treatment, P_R = success proportion of reference treatment.

Let

- 1. n_T = sample size of test treatment group
- 2. $cn_T =$ number of subjects with success in test treatment group
- 3. n_R = sample size of reference treatment group
- 4. $cn_R =$ number of subjects with success in reference treatment group

$$\hat{P}_T = {cn_T / n_T}, \ \hat{P}_R = {cn_R / n_R},$$

Confidential

and
$$se = \left(\frac{\hat{P}_R(1 - \hat{P}_R)}{n_R} + \frac{\hat{P}_T(1 - \hat{P}_T)}{n_T} \right)^{1/2}$$

The 90% confidence interval will be estimated using Wald's method with Yates' continuity correction, as:

$$L = (\hat{p}_{T} - \hat{p}_{R}) - 1.645 \text{ se} - (1/n_{T} + 1/n_{R})/2$$
$$U = (\hat{p}_{T} - \hat{p}_{R}) + 1.645 \text{ se} + (1/n_{T} + 1/n_{R})/2$$

 H_0 will be rejected if $L \geq$ -0.20 and $U \leq 0.20$ resulting in accepting H_A and concluding bioequivalence of the two products.

Tthe following SAS code will be used to test bioequivalence:

```
proc freq data = dataset;
tables treat*outcome/ riskdiff (Equiv correct);
run;
```

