4 STUDY OBJECTIVE AND ENDPOINTS

4.1 Study Objectives

The primary objective of this study is:

• To compare the clinical efficacy of anogenital warts treatment of patients treated with Podofilox Topical Gel 0.5% and patients treated with Condylox® Gel 0.5% to patients treated with placebo (superiority comparisons), and to compare efficacy of Podofilox Topical Gel 0.5% with that of Condylox[®] Gel 0.5% (bioequivalence comparison).

The secondary objective of this study is:

• To demonstrate safety of Podofilox Topical Gel 0.5% compared to Condylox[®] Gel 0.5% or placebo assessed by the frequency and severity of adverse events and application site reaction scores (erythema, dryness, burning/stinging, erosion, edema, pain, itching and bleeding).

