5.3 Sample Size Considerations

Approximately 413 subjects (177 in each active arm and 59 in placebo group) will be enrolled to obtain at least 392 mITT subjects (168 in each active treatment arm and 56 in placebo group) and to complete 350 PP subjects (150 in each active arm and 50 in placebo group). This sample size was calculated assuming that both active treatments would have equivalent success rates of 40% and placebo would have a success rate of 15%. This sample size will provide an overall probability of at least 0.9 of having the 90% Wald confidence interval, with Yates' continuity correction, of the difference between the test and reference success rates contained within the interval -0.20 to +0.20 in the PP population, in addition to establishing that the success rates for both active treatments are statistically greater than that of the placebo arm (two-sided continuity-corrected Z-tests, $\alpha = 0.05$) in the mITT population.

mITT (T:R:Placebo)	Prob. of Superiority*	of Superiority* PP (T:R:Placebo) Prob.		Prob. of study success
168:168:56 (392)	0.98	150:150:50 (350)	0.92	0.90

*) Superiority analysis based on two-sided, α = 0.05, continuity-corrected Z-tests.

**) Bioequivalence (BE) analysis based on 90% confidence interval (CI) of the difference between Test and reference for proportions of subjects with treatment success, calculated by the Wald's method with Yates' continuity correction.

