9.1.2 Superiority Analysis

Superiority will be assessed through continuity-corrected Z-tests comparing each active treatment to placebo. If both the test and RLD success proportions are statistically significantly greater than the placebo proportion (p<0.05) then they will be considered superior to the placebo. The results in the mITT population will be considered definitive and those in the PP population will be considered supportive.

For each treatment (Test and RLD) the Hypothesis to be tested is:

 $H_0: p_t - p_p \leq 0$

 $H_a: p_t - p_p > 0$

Where p_t = Proportion of cure for Treatment, and p_p is proportion of cure for Placebo.

The rest of the formulation is the similar to the one for Equivalence assessment, using 95% Confidence Interval. For testing the superiority, the following SAS code will be used:

proc freq data = dataset;

Confidential

```
tables treat*outcome/ riskdiff (Equal correct);
run;
```

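### The joint success criterion used for power in SAP 5.3 (equivalence interval plus both actives superior to placebo) is never made a condition of the bioequivalence conclusion

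*SAP*

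**What the plan says.** **Decision rule.** SAP 9.1.1: "Bioequivalence between the test and the reference product will be established if the 90% confidence interval for the difference in success proportions" is inside [-0.20, +0.20]. The null is rejected on the two bounds L and U alone, "concluding bioequivalence of the two products". Protocol 8.3.2 gives the same rule. Protocol 8.2 and both synopses also establish therapeutic equivalence from the interval alone. PP is definitive and mITT supportive.

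**Superiority.** SAP 9.1.2 and protocol 8.3.3 test each active against placebo, with mITT definitive. The only consequence given is that if both are "statistically significantly greater than the placebo proportion (p<0.05) then they will be considered superior to the placebo". Nothing says what follows if either test fails.

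**Objective.** SAP 4.1 puts both comparisons in the primary objective: the two actives are compared "to patients treated with placebo (superiority comparisons), and to compare efficacy of Podofilox Topical Gel 0.5% with that of" the reference.

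**Planned analysis.** SAP 6 lists superiority and bioequivalence as two bullets and does not link them. The results go to separate tables (14.2.3.1.1 and 14.2.2.1.1).

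**Power.** SAP 5.3: "This sample size will provide an overall probability of at least 0.9 of having the 90% Wald confidence interval" within the limits in PP, "in addition to establishing that the success rates for both active treatments are statistically greater than that of the placebo arm" in mITT. Its table gives superiority 0.98, interval 0.92 and "Prob. of study success" 0.90.

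**The concern.** The placebo arm is there to show that the trial could have detected a difference. If neither gel separates from vehicle in this trial, the test-reference difference is near zero and the interval is met almost automatically. Under the wording of 9.1.1 that trial ends in a conclusion of bioequivalence, although it does not meet the event on which SAP 5.3 sized the study. The failed superiority test would still appear in its own table, and no estimate or p-value would change. What is left open is the trial's stated primary conclusion, and it should be fixed before anyone knows which case applies.

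**Working it through.** **Inputs.** Rates 40/40/15, PP 150:150:50 and mITT 168:168:56 (SAP 5.3). Yates-corrected Wald interval with unpooled standard error and 1.645 (SAP 9.1.1). Continuity-corrected Z-tests, two-sided 0.05 (SAP 5.3). Reference gel clearance of 38.4% and 25.6% in two cited trials (protocol 1.2.2).

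**1. The plan's own figures, by normal approximation**

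- Interval: se = √(2×0.40×0.60/150) = 0.0566. Then (0.20 − 1/150)/0.0566 − 1.645 = 1.773, and 2Φ(1.773) − 1 = 0.924. The stated 0.92 reproduces (0.928 by exact enumeration).
- One active against placebo, unpooled: se = √(0.40×0.60/168 + 0.15×0.85/56) = 0.0609. Uncorrected: 0.25/0.0609 − 1.96 = 2.147, giving 0.984. Corrected by (1/168 + 1/56)/2 = 0.0119: z = 1.951, giving 0.974.
- Both actives, corrected, with correlation 0.61 through the shared placebo arm: 0.956. By exact enumeration: 0.933 (unpooled Z) or 0.906 (pooled Z).
- Joint event: 0.98 × 0.92 = 0.90 is the plan's figure. With both corrected tests it is 0.956 × 0.924 = 0.88 by normal approximation, and 0.871 (unpooled) or 0.848 (pooled) exact.

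So the 0.98 fits a single active-placebo comparison, whereas the text of 5.3 requires both.

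**2. Interval alone against the joint criterion.** Exact enumeration, counting trials with L ≥ −0.20 and U ≤ 0.20. The 150 PP subjects are nested in the 168 mITT subjects, with equal success rates inside and outside PP.

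| Test/reference/placebo (%) | Interval alone | Joint, unpooled / pooled Z |
|---|---|---|
| 15/15/15 | 0.997 | 0.013 / 0.004 |
| 40/40/40 | 0.928 | 0.008 / 0.006 |
| 15/40/15 | 0.003 | 0.0003 / 0.0002 |
| 15/30/15 | 0.233 | 0.012 / 0.006 |
| 15/25.6/15 | 0.602 | 0.022 / 0.009 |
| 40/40/15 | 0.928 | 0.871 / 0.848 |
| 38.4/38.4/15 | 0.932 | 0.846 / 0.810 |
| 30/30/15 | 0.956 | 0.513 / 0.409 |
| 25.6/25.6/15 | 0.972 | 0.272 / 0.189 |

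The first two rows have no active effect. The next three have an inactive test gel. With the reference at 30% or 25.6%, the true differences of 15 and 10.6 points lie inside the 20-point margin, so the interval alone cannot be relied on to screen out an inactive gel.

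**3. Sensitivity to size.** Site 201 is excluded from the definitive PP and mITT sets (SAP 6 and 7.5.1), and the documents do not give its size. Assuming 110 PP subjects per active arm, the interval alone is met in 0.79 of trials with both actives at 40% and in 0.48 for 15/25.6/15. The levels move and the pattern does not.

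**The case against.** A reader might infer that SAP 5.3 and 9.1.1 contradict each other. They do not. The footnote in 5.3 defines the bioequivalence analysis as the 90% interval alone and gives it a separate 0.92; study success is a different, joint quantity. The gap is that the joint quantity has no operative counterpart outside the power section.

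A reader might also infer that SAP 6 concludes bioequivalence from the interval alone. Its wording states a requirement on the interval and sets superiority beside it, so the criticism there is only the missing link.

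Nor is superiority missing or hidden. It belongs to the primary objective, and its tests, population, alpha and both-must-win condition are pre-specified. A failure would be reported.

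The scenarios with large effects depart from the plan. At its 40% reference rate an inactive gel passes in 0.3% of trials, and at the cited 38.4% in 0.7%. The 60% figure pairs a 25.6% rate, from a gel-versus-solution trial with no vehicle arm described, with a 15% vehicle rate, which is an assumption.

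Finally, it would be too strong to say that 0.98 cannot be obtained: one uncorrected unpooled comparison gives 0.984 by normal approximation.

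These points narrow the concern but do not answer it. Intent can be inferred from SAP 4.1 and 5.3, yet the only sentences that state a conclusion are unconditional.

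**Conclusion.** The concern holds in this limited form: the plan concludes bioequivalence from the test-reference interval, and the joint criterion it was powered on is not carried into that conclusion. With no active effect in any arm, the written rule gives a bioequivalence conclusion in 92.8% (all arms at 40%) to 99.7% (all at 15%) of trials, against roughly 1% or less under the joint criterion. The exposure is small if the planned rates hold. It grows if vehicle response is higher or reference response lower than planned.

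The figures rest on the planned sample sizes before removal of site 201, on equal success rates inside and outside PP, and on a Z-test whose variance form is not firmly stated, hence the paired values.

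A separate, smaller point also stands. With both corrected tests required, as SAP 5.3 words it, the overall probability is about 0.85-0.87 exact (0.88 by normal approximation), not at least 0.9.

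**What to change.** Before unblinding:

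1. Keep the 9.1.1 interval as the equivalence criterion, so the 0.92 in SAP 5.3 stands.
2. State in SAP 6 and 9.1 that the final bioequivalence conclusion requires (a) the PP 90% interval within [-0.20, +0.20] and (b) test and reference each superior to placebo in mITT (continuity-corrected Z, two-sided p<0.05). If (b) fails, report the interval without a bioequivalence conclusion.
3. Replace the unconditional concluding wording in SAP 9.1.1 and protocol 8.3.2 with a cross-reference to that statement, and align protocol 8.2 and both synopses.
4. Confirm the variance form of the Z-test. SAP 9.1.2 says only "The rest of the formulation is the similar to the one for Equivalence assessment, using 95% Confidence Interval", which points loosely to the unpooled standard error. Then restate the 0.98 and 0.90 in SAP 5.3.

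No new data, dataset or test is needed. All conditions must hold, so no alpha adjustment is needed either.

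The real cost is lost claims when the products are truly equivalent and both beat placebo, because placebo has only 56 mITT subjects. At 40/40/15 the probability of the claim falls from 0.93 to 0.87 (unpooled) or 0.85 (pooled). If every mITT subject outside PP counts as a failure through LOCF, it falls to 0.84 or 0.79. At 25.6/25.6/15 it falls from 0.97 to 0.27 or 0.19 (equal rates inside and outside PP). The sponsor should accept that loss knowingly; it follows from the criterion on which SAP 5.3 already sized the trial.
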